2.1.4.4 Pharmacodynamic variables (lipid variables)

Lipid parameters include LDL-C, Total-C, HDL-C and TG. Each parameter will be assessed at baseline (Day 1), Week 4, Week 8, Week 12 and Week 16 during the treatment period (on-treatment estimand) as defined in [Section 2.1.4.5](#). Post-treatment data will not be considered.

The pharmacodynamic endpoints will be the percent change in LDL-C, Total-C, HDL-C, and TG values from baseline to Week 4, Week 8, Week 12 and Week 16.

All calculated and measured LDL-C, Total-C, HDL-C, and TG values (scheduled or unscheduled, fasting or not fasting) may be used in the analyses if appropriate according to above definition and analysis windows (as defined in [Table 1](#)) used to allocate a time point to a measurement. In case both calculated and measured LDL-C are provided for the same sampling, the measured LDL-C will be considered. For TG, only fasting measurements will be used, measurements with missing fasting status will be excluded from the analyses.

2.1.4.5 Safety endpoints

The safety analysis will be based on the reported adverse events including SAE AESIs and other safety information, such as clinical laboratory data and vital signs.

Observation period

The period of safety observation starts from the time when the patient gives informed consent and is divided into the following periods:

- The pre-treatment period: defined as the time from the signed informed consent up to the first IMP injection;

- The TEAE period of the parallel-arm period defined as the time from the first IMP injection to the day before the second IMP injection for patients entering into the single arm period or to 70 days after the first IMP injection, whichever comes first;
 - The TEAE period of the parallel-arm period will include the TREATMENT period defined as the time from the first IMP injection to the day before the second IMP injection for patients entering into the single arm period, or to 35 days after the first IMP injection, whichever comes first.
- The TEAE period of the single-arm period is defined as the time from the second IMP injection up to the day of last IMP injection + 70 days.
 - The TEAE period of the single-arm period will include the TREATMENT period defined as the time from the second IMP injection up to the day of last IMP injection + 35 days.
- The post-treatment period: defined as the time starting 71 days after the day of last IMP injection.

The on-study observation period of the parallel-arm period is defined as the time from the day of first IMP injection until the Week 4 visit of the patient, if done, or 4 weeks after the randomization of the patient.

The on-study observation period of the single-arm period is defined as the time from the second IMP injection until the Week 16 visit of the patient, if done, or 16 weeks after the randomization of the patient.

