- j Injection Experience questionnaire: Completed by the patient after each self-injection (AI or SYDNEY) addressing specific aspects of using the device.
- k Blood pressure after 5 minutes in seating resting position.
- l Total bilirubin (and, in case of values above the normal range, differentiation in conjugated and non-conjugated bilirubin).
- m Hematology includes: red blood cell count, hematocrit, hemoglobin, white blood cell count with differential count (neutrophils, eosinophils, basophils, monocytes, and lymphocytes), and platelets. Biochemistry includes: sodium, potassium, chloride, plasma glucose, calcium, urea nitrogen, creatinine, total proteins, albumin, γ GT.
- n When alirocumab is to be administered, PK samples will be taken prior to alirocumab injection (Includes assay of total and free PCSK9).
- o Prior to dosing with any IMP.

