- Remind patient to be in fasting conditions (ie overnight, at least 10 to 12 hours fast and refrain from smoking) for next study visit (Visit 6). Also, alcohol consumption within 48 hours and intense physical exercise within 24 hours preceding the next visit are discouraged

10.1.4 Visit 6: Day 29 \pm 3 days, Week 4

This visit may be performed on site or as a home-visit.

The following procedures will be performed:

- Record vital signs including systolic and diastolic blood pressure (measured after 5 minutes in a seated resting position) and heart rate
- Record concomitant medications
- Record AEs (including SAE and AESI)

- Obtain fasting blood samples for:
 - Lipids panel
 - Liver function panel
 - CPK
 - Pharmacokinetics: PK parameters including assay of total and free PCSK9
 - Detection of anti-alirocumab antibodies.
- Contact IRT for allocation of a kit number for SYDNEY
- Record the kit number allocated in the e-CRF
- Dispense the SYDNEY device to the patient if the injection is to be administered on site or to the Visiting Nurse, if the injection to be administered at home
- Dispense patient diary, to be completed after the injection
- Dispense Injection Experience Questionnaire, to be completed after the injection
- Collect and return the study supplies and diary (performed by the Visiting Nurse if the visit is completed at home)
- Confirm scheduled visit for Week 8 (Day 57 [\pm 3 days], Visit 7)
- Remind patient to be in fasting conditions (ie overnight, at least 10 to 12 hours fast and refrain from smoking) for next study visit (Vist 7). Also, alcohol consumption within 48 hours and intense physical exercise within 24 hours preceding the next visit are discouraged
- Review patient diary and record patient complaint (including PTC) in the Patient complaints form (for the Week 4 injection), if any (as described in [Section 9.1](#)), after received from the patient or theVisiting Nurse.

10.1.5 Visit 7: Day 57 \pm 3 days, Week 8

This visit may be performed on site or as a home-visit.

The following procedures will be performed:

- Record vital signs including systolic and diastolic blood pressure (measured after 5 minutes in a seated resting position) and heart rate
- Record concomitant medications
- Record AEs (including SAE and AESI)
- Obtain fasting blood samples for:
 - Lipids panel
 - Liver function panel
 - CPK

- Pharmacokinetics: PK parameters including assay of total and free PCSK9.

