11.3 ANALYSIS POPULATIONS

11.3.1 Modified intent-to-treat populations

The primary efficacy analysis population that will be used for the analyses of LDL-C will be the modified intent-to-treat (mITT) population.

The mITT population of the parallel arms period will consist of all randomized patients who receive at least 1 dose or part of a dose of IMP visit during this period and who had an evaluable value of LDL-C at baseline and an on-treatment LDL-C value within Week 4 analysis window. The treatment period for the parallel arms period is defined as the time period from the first IMP injection up to 35 days after this injection or up to the day before the second injection, whichever comes first. Patients in this mITT population will be analyzed according to the auto-injector device group allocated by randomization (ie, as-randomized treatment group).

The mITT population of the single-arm period will consist of all randomized patients who continue in single-arm period and receive at least 1 dose or part of a dose of IMP of this period and who had an evaluable value of LDL-C at baseline and at least one on-treatment LDL-C within one of the analysis windows from Week 8 to Week 16. The treatment period for the single-arm period is defined as the time period from the second IMP injection up to 35 days after the last IMP injection for patients entering into the single arm period.

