11.4.4 Analyses of safety data

Safety data will be presented on the safety population of the parallel-arm period and of the single-arm period. Treatment-emergent adverse events (TEAEs), treatment-emergent SAEs, treatment-emergent AESIs, and TEAEs leading to treatment discontinuation, will be summarized based on the Medical Dictionary for Regulatory Activities (MedDRA) coding of verbatim terms reported by investigators (Section 9.2.5).

All safety analyses will be performed using the following common rules:

- The observation period to be used for the safety population is the TEAE period. The TEAE period is defined
 - For the parallel-arms period as the time from the first IMP injection to the day before the second IMP injection (for patients entering into the single arm period period) or to 70 days after the first IMP injection, whichever comes first
 - For the single-arm period as the time from the first IMP injection received in the single arm period to 70 days after the last IMP injection.

The following definitions will be applied to laboratory parameters, and vital signs:

- The potentially clinically significant abnormality (PCSA) values are defined as abnormal values considered medically important by the Sponsor according to predefined criteria/thresholds based on literature review and defined by the Sponsor for clinical laboratory tests, and vital signs.
- Potentially clinically significant abnormality criteria will determine which patients had at least 1 PCSA during the TEAE period, taking into account all evaluations performed, including unscheduled or repeated evaluations. The number of all such patients will be the numerator for the on-treatment PCSA percentage.

- Treatment period: the treatment period used for quantitative analysis is defined:
 - For the parallel-arms period as the time from the first IMP injection to 35 days after this injection or to the day before the second IMP injection (for patients entering into the single arm period period) whichever comes first.
 - For the single-arm period as the time from the first IMP injection received in the single arm period to 35 days after the last IMP injection.

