2.3.1 Modified intent-to-treat population

The mITT population of the parallel arms period will consist of all randomized patients who received at least 1 dose or part of a dose of IMP during this period and who had an evaluable value of LDL-C at baseline and an on-treatment LDL-C value within Week 4 analysis window. Patients in this mITT population will be analyzed according to the auto-injector device group allocated by randomization (ie, as-randomized treatment group).

The mITT population of the single arm period will consist of all randomized patients who continued in single arm period and received at least 1 dose or part of a dose of IMP during this period and who had an evaluable value of LDL-C at baseline and at least one on-treatment LDL-C within one of the analysis windows from Week 8 to Week 16.

The treatment periods are defined in [Section 2.1.4.5](#).

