2.4.4.2.2 Pharmacokinetic variables

All analyses for PK variables will be presented by treatment group for the parallel-arms period and overall for the single-arm period.

All the PK analyses will be performed using the PK population in each period.

PK parameters (C_{max} , t_{max} , AUC_{0-tau} and C_{trough}) will be summarized (mean, geometric mean, median, standard deviation, standard error of mean, coefficient of variation, minimum, and maximum).

For the parallel-arms period, log-transformed C_{max} , AUC_{0-tau} and C_{trough} , estimates and 90% CI for the ratio of geometric means (SYDNEY/ AI) will be provided using an ANCOVA model with treatment group (SYDNEY, AI) as fixed effect and baseline body weight as covariate.

2.4.4.2.3 *Anti-drug antibodies variables*

The following summaries will be performed on the ADA population by treatment group for the parallel-arm period and overall for the single-arm period, taking into account all samples regardless of timing in relation to injections:

- ADA results (negative or positive) by time point
- ADA titers using descriptive statistics (median, minimum, and maximum) for positive ADA by time point
- Number (%) of patients with pre-existing ADA and number (%) of patients with treatment emergent ADA positive response
- Number (%) of patients with persistent/indeterminate /transient treatment-emergent ADA positive response
- Time to onset of treatment-emergent ADA positive response using descriptive statistics.

2.4.4.2.4 *Pharmacodynamic variables (lipid variables)*

Continuous endpoints anticipated to have a normal distribution

Continuous variables anticipated to have a normal distribution (ie, percent change in LDL-C, Total-C, HDL-C at Week 4) will be analyzed in the mITT population of the parallel-arm period using an ANCOVA model with fixed categorical effect of treatment group (SYDNEY, AI), as well as the continuous fixed covariate of corresponding baseline value. LS means and 95% CI will be provided for both SYDNEY and AI.

Depending on the number of missing LDL-C values at Week 4, a sensitivity analysis may be performed using multiple imputations (with baseline LDL-C and device group factors included in the imputation model) using the MI SAS® procedure to impute missing data followed by ANCOVA model. Results will be combined using Rubin's formulae with the SAS MIANALYZE procedure.

Continuous endpoints anticipated to have a non-normal distribution

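### The parallel-arm treatment period ends the day before the Week 4 dose, so the pre-dose Week 4 lipid sample falls outside it and the SYDNEY versus AI lipid comparison loses nearly all its patients

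*SAP*

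**What the plan says.** SAP 2.1.4.5 gives this definition of the parallel-arm treatment period: "the time from the first IMP injection to the day before the second IMP injection for patients entering into the single arm period". A 35-day cap, counted from the first injection, applies where it is reached sooner. Protocol 11.3.1 has the same boundary ("up to 35 days after this injection or up to the day before the second injection, whichever comes first"), and so does protocol 11.4.4 ("to 35 days after this injection or to the day before the second IMP injection"). The parallel-arm TEAE period stops at the same point, with a 70-day cap. Both single-arm periods start at the second injection.

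Three SAP provisions then depend on that boundary:

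- SAP 2.1.4.4 restricts lipid values to that period, in the words "during the treatment period (on-treatment estimand) as defined in", with a link to 2.1.4.5.
- SAP 2.3.1 admits a patient to the parallel-arm mITT population only with "an on-treatment LDL-C value within Week 4 analysis window".
- SAP 2.4.4.2.4 covers Week 4 percent change in LDL-C, Total-C and HDL-C; these variables, it says, "will be analyzed in the mITT population of the parallel-arm period using an ANCOVA model". Triglycerides are analysed in the same population by robust regression.

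The flow chart (protocol 1.2) schedules lipids at screening, Day 1 and Weeks 4, 8, 12 and 16. Footnote o times the Week 4 sample: "Prior to dosing with any IMP". Protocol 10.1.4 lists the lipid draw at Visit 6 and, at the same visit, "Dispense the SYDNEY device to the patient if the injection is to be administered on site or to the Visiting Nurse" for a home injection. Footnote f has the nurse bring the blood-draw supplies and the kit to one home visit and take the used material away after the injection.

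**The concern.** The Week 4 sample and the second injection belong to the same visit, with the sample first. A period that closes the day before the injection therefore closes before the sample is taken. The single-arm period does not pick the sample up either: it opens at the injection, and its lipid summaries cover Weeks 8 to 16 only.

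This is the only between-device lipid comparison in the study, and it answers a stated secondary objective. Applied as written, it would run on a handful of patients, mostly selected by having stopped treatment.

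The same boundary governs the parallel-arm PCSA counts, the last and worst on-treatment values (SAP 2.4.4.2.5), and the proportions with LDL-C below 25 and 15 mg/dL (SAP 2.1.5). For liver panel, CPK and vital signs, Week 4 is the only scheduled post-baseline assessment in the parallel-arm period. Those values would drop out of these summaries. If a programmer instead assigned them by calendar date, AI patients' values would be counted in the SYDNEY single-arm period.

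**Working it through.** **Inputs.** Visit 6 is Day 29 ± 3 (flow chart; protocol 10.1.4). The period end is as quoted above. The Week 4 analysis window is Days 15 to 42 (SAP 2.5.4). There are six lipid samples per patient (protocol 9.3). The plan is 66 randomized, 33 per arm, for 60 evaluable at 10% drop-out (protocol 11.1). The plan gives no figure for the size of the Week 4 lipid comparison. Its overall numbers are consistent: 66 × 0.90 = 59.4, about 60.

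**Step 1: dates.** Period end = min(dose day − 1, Day 1 + 35 = Day 36).

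| Second dose and pre-dose draw (day) | 26 | 27 | 28 | 29 | 30 | 31 | 32 |
|---|---|---|---|---|---|---|---|
| Treatment period ends (day) | 25 | 26 | 27 | 28 | 29 | 30 | 31 |

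The draw is one day late in 7 of 7 cases. The Day 36 cap never applies to a patient dosed within the visit window.

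**Step 2: other samples.** Of the six scheduled lipid samples, one falls in Days 15 to 42, and it is the Visit 6 sample. None falls between Day 15 and the day before the dose, because Visits 4 and 5 draw PK blood only (protocol 10.1.3).

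**Step 3: who remains.** Patients with no second dose and an LDL-C by Day 36 still qualify, as does anyone with an unscheduled or earlier-day sample. The documents do not say how many patients miss the second dose. Assuming 0 to 10%: 66 × 0 = 0 to 66 × 0.10 = 6.6 patients, or at most 33 × 0.10 = 3.3 per arm.

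**Step 4: precision.** The ANCOVA has two groups and one covariate. With baseline taken as balanced, the 95% CI half-width in residual SD units is t(0.975, N − 3) × √(1/n₁ + 1/n₂):

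- 33 + 33: 1.998 × 0.246 = 0.49
- 30 + 30 (the planned evaluable number): 0.52
- 4 + 3: 2.776 × 0.764 = 2.12
- 3 + 3: 3.182 × 0.816 = 2.60

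Against 33 per arm, 3 + 3 is 2.60 / 0.492 = 5.3 times wider and 4 + 3 is 2.12 / 0.492 = 4.3 times wider. With no qualifying patients there is no estimate.

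**Step 5: possible rescues in the text.**

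- Protocol 9.2.4.1 identifies the Week 4 value by its analysis window alone, but this leaves the on-treatment condition for mITT entry in place.
- The optional multiple imputation in SAP 2.4.4.2.4 cannot help if run within the mITT population, because entry already needs a Week 4 value.
- The on-study period in SAP 2.1.4.5 reaches the Week 4 visit, but it is used only to classify deaths.
- The missing-time rule for assessments in SAP 2.5.3 covers baseline only.
- SAP 1.5 and 1.6 record no modification.

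**Not affected.** The primary PTC endpoint and the safety population do not depend on this boundary. The PK comparison uses e-CRF visits. By-visit safety summaries in the SAP use analysis windows. ADA summaries are largely protected, because SAP 2.4.4.2.3 counts samples whatever their timing relative to dosing.

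**The case against.** The strongest reply is that nobody would apply the rule this way. Protocol 9.2.4.1, the on-study period and the wording on imputation all assume that the Week 4 values are available. The comparison is secondary, protocol 4.2.2 calls it descriptive, and an almost empty analysis population would be seen at the first programming run. All of this is fair as evidence of intent. It does not change the rule: to get the intended analysis a programmer must depart from the written population definition, without documentation, in an open-label study.

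A second reply is that same-day dosing is not certain. The flow chart marks no device collection or compliance check at Week 4. Footnote g reviews the Week 8 injection at Week 12. Protocol 8.1.2 asks patients to refrigerate the product, and parts of 10.1.5 and 10.1.6 read like take-home dosing. A sample taken on a day before the injection would indeed count. For Week 4, however, footnote f, protocol 6.1 and protocol 10.1.4 put draw and injection at one visit, so same-day dosing is the reading to plan on.

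Three narrower points stand. The 0 to 10% range is an assumption; the plan's drop-out figure covers the whole study. The loss of precision depends on the split, so 4 + 3 belongs beside 3 + 3. Counting AI patients' values under SYDNEY would happen only if values were assigned by calendar date, which the documents do not prescribe; under the written rule those values fall in neither period.

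**Conclusion.** The concern holds: the rule is wrong as written. For every permitted Week 4 visit day the scheduled lipid sample lies one day outside the parallel-arm treatment period, and no other scheduled sample can replace it. The Week 4 comparison then rests on 0 to about 6 or 7 of 66 patients, plus any with an unscheduled or earlier-day sample. At best its confidence interval is roughly four to five times wider than intended, and at worst there is no estimate. Up to 33 AI patients' Week 4 liver, CPK and vital-sign values are also left without a clear period in the PCSA and last/worst summaries.

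The date result assumes that the sample and second injection fall on the same day. The patient numbers assume 0 to 10% without a second dose, and the half-widths assume balanced baseline values. The intent is not in doubt, but a stated secondary analysis cannot be produced by following the plan, so this must be corrected before database lock.

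**What to change.** In SAP 2.1.4.5 and protocol 11.3.1 and 11.4.4, end the parallel-arm treatment and TEAE periods immediately before the date and time of the Week 4 SYDNEY dose, and start the single-arm periods at that dose. Keep the 35-day and 70-day caps. State that the Week 4 visit lipid samples, and laboratory and vital-sign values taken before the dose that day, belong to the parallel-arm period. The SAP already bounds baseline by date and time of first administration, so this follows its own convention.

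Add a missing-time rule for the day of the second dose: scheduled Visit 6 assessments go to the parallel-arm period, and adverse events with unknown onset time go to the single-arm period. The lipid comparison alone would need only the sentence on pre-dose values; moving the TEAE boundary as well closes the PCSA gap.

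With this change the scheduled sample is on-treatment for all seven visit days, and the comparison keeps its planned 60 or so patients, with a half-width of about 0.52 SD.

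The cost is wording in three places, one date-time derivation and one convention, with no new data and no change to visits. The protocol wording would need an amendment under protocol section 15, which requires ethics committee approval. The downside is small: a few untimed values taken after the dose may be placed in the parallel-arm period, and a few adverse events that began before it may be counted under SYDNEY.
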